#### **9.4.4 Efficacy Analyses**

All efficacy analyses will be performed on the Efficacy Evaluable Set.

##### **9.4.4.1 Alive and Free of Respiratory Failure**

The proportion of participants alive and free of respiratory failure will be assessed at Days 14 and 28. Point estimates and their 90% confidence intervals (using Wald method with continuity correction) will be calculated.

Only the participant's survival status and respiratory failure (as defined in Section 8.1.1.1) status on Days 14 and 28 will be considered for this endpoint. If they experience respiratory failure after enrollment but recover by Days 14 or 28, per the definition of respiratory failure, they will be considered alive and free of respiratory failure at these time points.

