### Efficacy

All efficacy analyses will be performed on the Efficacy Evaluable Set. For the proportion of participants alive and free of respiratory failure at Days 14 and 28, point estimates and their 90% confidence intervals will be calculated. Summary statistics (n, mean, median, standard deviation, minimum, and maximum) will be presented for the percent change from baseline in CRP at the specified time points. Time to improvement defined as time to clinical improvement of at least 2 points (from first dose date) on a 9-point category ordinal scale, live discharge from the hospital, or considered fit for discharge (a score of 1 or 2 on the ordinal scale), whichever comes first, by Day 28 (this will also define the “responder” for the response rate analyses), will be analyzed using the Kaplan-Meier method.

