### **5.1 Inclusion Criteria**

Participants are eligible to be included in the study only if **all** of the criteria below apply.

1. Participant or legally authorized representative must be able to understand the purpose and risks of the study and provide written informed consent and authorization to use protected health information (in accordance with national and local patient privacy regulations).

2. Male or female participants at least 18 years of age at the time of signing the informed consent.
3. Participants who are hospitalized with coronavirus (SARS-CoV-2) infection, confirmed by PCR test or other commercial or public health assay in any specimen, as documented by either of the following:
  - a) PCR positive in sample collected < 72 hours prior to first dose, OR
  - b) PCR positive in sample collected  $\geq$  72 hours prior to first dose (but no more than 14 days prior to first dose), documented inability to obtain a repeat sample (eg, due to lack of testing supplies, limited testing capacity, results taking > 24 hours, etc), AND progressive disease suggestive of ongoing SARS-CoV-2 infection.
4. Evidence of respiratory failure attributable to COVID-19 pneumonia (documented radiographically) before enrollment where respiratory failure is defined based on resource utilization of any of the following modalities:
  - a) Endotracheal intubation and mechanical ventilation.
  - b) Oxygen delivered by high-flow nasal cannula (heated, humidified, oxygen delivered via reinforced nasal cannula at flow rates > 20 L/min with fraction of delivered oxygen  $\geq$  0.5).
  - c) Noninvasive positive pressure ventilation or continuous positive airway pressure.
  - d) Extracorporeal membrane oxygenation.
5. Nasogastric tube or other types of oral or percutaneous gastric feeding tube; placement must be radiographically confirmed and expected to remain in place, as judged by the Investigator, for a minimum of 3 days after study enrollment.
6. Has received treatment with PPIs (eg, omeprazole, esomeprazole, lansoprazole, dexlansoprazole, rabeprazole, or pantoprazole) for a minimum of 24 hours immediately prior to enrollment; any PPI will be permitted, provided it meets the minimum equivalent daily dose of 20 mg rabeprazole.
7. Willing to follow contraception guidelines when discharged from the hospital (Appendix F).

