### 9.2 Sample Size Determination

A sample size of 16 evaluable participants with COVID-19 was chosen based on the desire to gain adequate information while exposing as few participants as possible to the study procedures and study intervention. Given the inherent variability in the COVID-19 patient population, broad inclusion and exclusion criteria, and possible variability in treatment duration and PPI usage, approximately 20 participants will be enrolled in the study in order to have at least 16 evaluable participants able to complete PK Visit 2 (allowing for ~25% dropout rate due to disease progression).

**Note:** “Enrolled” means a participant’s, or his/her legally acceptable representative’s, agreement to participate in a clinical study following completion of the informed consent process. Potential participants who are screened for the purpose of determining eligibility for the study but are not randomly assigned/assigned in the study, are considered “screen failures”, unless otherwise specified by the protocol.

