**Table 9 Populations for Analysis**

Population/Analysis set	Description
PK Analysis Set	The PK Analysis Set will include all participants who received $\geq 1$ dose of acalabrutinib and had $\geq 1$ post-dose evaluable PK data point for acalabrutinib. The population will be defined by AstraZeneca, the pharmacokineticist, and the statistician prior to any analyses being performed.
Safety Analysis Set	The Safety Analysis Set will include all participants who received $\geq 1$ dose of study intervention
Efficacy Evaluable Set	The Efficacy Evaluable Set will include all participants who received $\geq 1$ dose of study intervention

ITT = intent to treat; PK = pharmacokinetic; PPI = proton-pump inhibitor.

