### 9.4.1 General Considerations

For efficacy continuous endpoints, the baseline is defined as the last observation prior to the first dose of acalabrutinib suspension.

No missing data imputation will be applied for efficacy analysis.

For safety analysis, where individual data points are missing because of dropouts or other reasons, the data will be summarized based on reduced denominators.

Sensitivity analysis may be done by excluding participants with significant protocol deviations as appropriate.

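### The 90% Wald interval with continuity correction for the proportion alive and free of respiratory failure breaks down when few, or nearly all, of about 20 participants succeed

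*Protocol*

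**What the plan says.** Section 9.4.4.1 of the Protocol sets the endpoint and the method: "The proportion of participants alive and free of respiratory failure will be assessed at Days 14 and 28", and "Point estimates and their 90% confidence intervals (using Wald method with continuity correction) will be calculated". The synopsis (Section 1.1, Efficacy) gives the level but no method: "point estimates and their 90% confidence intervals will be calculated". Neither place gives a rule for limits outside 0 to 1, an alternative for small counts, or an expected proportion.

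The denominator comes from three places. Section 9.2 says that "approximately 20 participants will be enrolled in the study in order to have at least 16 evaluable participants able to complete PK Visit 2". The margin for losses is described there as "allowing for ~25% dropout rate due to disease progression". Table 9 in Section 9.3 defines the set used here: "The Efficacy Evaluable Set will include all participants who received" at least one dose. Section 9.4.1 adds: "No missing data imputation will be applied for efficacy analysis". So the efficacy denominator is about 20, and smaller if participants with a missing Day 14 or Day 28 status are left out. The figure of 16 is the target for PK-evaluable participants, not the efficacy denominator.

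All participants start without the favourable outcome. Inclusion criterion 4 in Section 5.1 requires "Evidence of respiratory failure attributable to COVID-19 pneumonia (documented radiographically) before enrollment".

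**The concern.** The Wald interval takes its width from the estimated variance p(1-p)/n, which shrinks to zero as the observed proportion approaches 0 or 1. The continuity correction then adds only 1/(2n) on each side. With about 20 participants, all in respiratory failure at entry, a low count is possible, mainly at Day 14. At such a count the interval can be far too narrow and can extend below zero.

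Section 9.1 plans no hypothesis test for efficacy, so this interval is the only stated measure of uncertainty for the endpoint. If it is misleadingly tight at low counts, a reader would take the rate to be known much better than it is.

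**Working it through.** **Inputs.** Two-sided 90% level, so z = 1.6449 (Section 9.4.4.1). The planned enrolment of 20 equals 16 × 1.25 (Section 9.2). All dosed participants are analysed (Table 9), so n = 20 is the main case; n = 16 is shown for a reduced denominator. The true proportion is not in the documents, so every rate below is an assumption.

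**Formulas.** With x successes and p = x/n, the planned interval is p ± [z·√(p(1-p)/n) + 1/(2n)]. The exact (Clopper-Pearson) limits are the rates at which each binomial tail probability beyond x equals 0.05. Coverage at a true rate is the sum of the binomial probabilities of all x whose interval contains that rate.

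**Step 1: limits at n = 20.**

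| Successes | Planned interval | Exact interval |
|---|---|---|
| 0 | -2.5% to 2.5% | 0% to 13.9% |
| 1 | -5.5% to 15.5% | 0.3% to 21.6% |
| 2 | -3.5% to 23.5% | 1.8% to 28.3% |
| 3 | -0.6% to 30.6% | 4.2% to 34.4% |
| 4 | 2.8% to 37.2% | 7.1% to 40.1% |
| 10 | 29.1% to 70.9% | 30.2% to 69.8% |

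For 0/20 the variance term is zero, which leaves ±1/40 = ±2.5%. The exact upper limit is 1 - 0.05^(1/20) = 13.9%. By symmetry the upper limit exceeds 100% for 17 to 20 successes. At n = 16 the lower limit is also negative for 0 to 3 successes, and 0/16 gives -3.1% to 3.1% against an exact 0% to 17.1%.

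**Step 2: coverage of the planned interval, nominal 90%.**

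| Assumed true rate | n = 20 | n = 16 |
|---|---|---|
| 5% | 63.9% | 55.9% |
| 10% | 86.7% | 81.1% |
| 20% | 92.1% | 83.3% |
| 50% | 88.5% | 92.3% |

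The first entry can be traced by hand. At n = 20 only x = 1, 2, 3 and 4 give intervals that contain 5%, and their probabilities sum to 0.639. Most of the loss is x = 0, with probability 0.95^20 = 0.358. The same coverages hold at 95%, 90% and 80% by symmetry. Over true rates of 20% to 80% the minimum is 85.5% at n = 20 and 83.3% at n = 16. For rates too small to leave the interval at 0/20 (up to 2.5%), coverage is close to 100% (100% at a true 1%, 99.9% at 2%). Just above that point it falls to about 40%.

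**Step 3: what the correction contributes.** At a true 5% and n = 20, coverage is 63.9% with the correction and 62.6% without it.

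**Step 4: how often impossible limits would appear at n = 20.** This is the probability of 3 or fewer successes, since 17 or more is negligible at these rates: 87% at a true 10%, 65% at 15%, 41% at 20% and 11% at 30%.

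**Step 5: alternatives.** At n = 20 the exact interval covers 98.4% at a true 5%, 95.7% at 10%, 95.6% at 20% and 95.9% at 50%. Its minimum over 2% to 98% lies between 90.1% and 90.7% for the two sample sizes. Wilson is much better than the planned method near 0 (92.5% at a true 5%). In the middle it is not: at n = 20 it covers 84.4% at a true 20%, against 92.1% for the planned method, and its minimum over 20% to 80% is 84.3%, against 85.5%.

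**The case against.** The strongest reply is that the poor coverage depends on rates the protocol does not predict. Entry in respiratory failure does not imply that about 5% will be free of it at Day 14 or Day 28. High-flow oxygen and non-invasive ventilation also qualify for entry, and anyone recovered by the assessment day counts as a success. The one outcome figure cited, mortality of nearly 50% in ventilated patients (Section 2.2.1), does not say how many survivors are off support. At 20% to 80% the planned interval averages 91.6% coverage at n = 20. This stands. A reader might infer that the method fails outright at this sample size, or that 56% coverage is to be expected. The documents support neither: the first ignores the middle range, and the second combines an assumed 5% rate with the PK-evaluable target of 16.

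It can also be said that little depends on the interval. There is no efficacy test (Section 9.1), no formal interim efficacy or futility analysis (Section 9.5), and the stated aim is preliminary efficacy. That limits the consequence and is accepted.

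Finally, limits could be truncated to 0 and 1 when reported. That would hide the impossible values but would leave 0/20 as 0% to 2.5%, so the false precision remains.

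A reader might also extend the point to the response rate. Section 9.4.4.3 specifies only Kaplan-Meier estimates with 90% intervals and no binomial interval, so the extension has no basis in the text.

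**Conclusion.** The point holds in limited form. The protocol names a specific interval that gives wrong error bars at extreme counts. The limits in Step 1 are arithmetic and depend only on n; the coverages and probabilities depend on assumed true rates. At n = 20, coverage falls well below 90% only for rates below about 10% or above about 90%, apart from the very smallest and largest rates, where it is near 100%. Impossible limits reach further, with probability 41% at a true 20%. A denominator reduced by missing outcomes would make coverage worse at 5%, 10% and 20%. The endpoint is secondary and descriptive, so what suffers is the reported precision. The correction is worth making because it is simple and the planned method offers no compensating advantage.

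**What to change.** In Section 9.4.4.1, replace the named Wald method with exact (Clopper-Pearson) for the 90% intervals at Days 14 and 28, and carry the same wording into the SAP. The synopsis names no method and can stay as it is. Wilson should not be listed as equivalent, because its coverage drops to about 84% in the middle range.

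The cost is one phrase and a standard software option, with no effect on sample size, data collection or conduct. Exact intervals are mildly conservative, with coverage above the nominal 90%. Against the planned interval the loss is small: at 10/20 the exact width is 69.8 - 30.2 = 39.6 percentage points, compared with 70.9 - 29.1 = 41.8. The exact interval is clearly wider at 0/20, where the planned one is too narrow.

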##### **9.4.4.2 Percent Change in C-reactive Protein**

Summary statistics (n, mean, median, standard deviation, minimum, and maximum) will be presented for the percent change from baseline in CRP at Days 3, 5, 7, 14, and 28. Baseline is defined as the last observation prior to the first dose of acalabrutinib suspension.

##### **9.4.4.3 Time to Clinical Improvement on 9-point Ordinal Scale**

Time to improvement defined as time to clinical improvement of at least 2 points (from first dose date) on a 9-point category ordinal scale, live discharge from the hospital, or considered fit for discharge (a score of 1 or 2 on the ordinal scale), whichever comes first, by Day 28 (this will also define the "responder" for the response rate analyses), will be analyzed using Kaplan-Meier method with Kaplan-Meier estimates and their 90% confidence intervals. If a

participant did not have an improvement and did not drop out prior to Day 28, the data will be censored at Day 28. If a participant did not have an improvement but dropped out prior to Day 28, the data will be censored at the last date known that without improvement.

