### 2.2 Background

#### 2.2.1 Coronavirus Disease 2019

Coronavirus disease 2019 is a new pandemic disease caused by SARS-CoV-2, a novel coronavirus that originated from Wuhan, China. Most COVID-19 cases (~80%) are mild respiratory illnesses. However, moderate and severe COVID-19 cases require hospitalization and can progress quickly to severe acute lung injury and acute respiratory distress syndrome (Huang et al 2020, Zhou et al 2020), which can lead to death due to respiratory and cardiac failure. The death rate from COVID-19 across different populations range from 2.4% in China (updated data) to 7.2% in Italy (Livingston and Bucher 2020, Wu and McGoogan 2020), with the highest rate reported among older patients and those who are immunocompromised or have other comorbidities or lymphocytopenia (Guan et al 2020b, Livingston and Bucher 2020, Onder et al 2020, Wang et al 2020). The mortality rate in critically ill patients with COVID-19 (ie, those requiring mechanical ventilation) is nearly 50% (Wu and McGoogan 2020).

In patients with severe COVID-19, SARS-CoV-2-induced cytokine storm or “hyperimmune response” is hypothesized to cause immunopathologic damage to the lungs by modulating pulmonary macrophages and dendritic cells (Channappanavar et al 2016, Huang et al 2005, Wong et al 2004, Yoshikawa et al 2009), and/or neutrophils (Herold et al 2015). Putative inflammatory mediators include IL-1 $\beta$ , IL-6, IL-8, IL-10, TNF $\alpha$ , and MCP-1 (Chen et al 2020, Herold et al 2015, Yoshikawa et al 2009). Other risk factors for severe COVID-19 illness include the presence of neutrophilia, organ dysfunction (elevated lactate dehydrogenase), coagulation abnormalities, thrombocytopenia, and lymphocytopenia, suggesting findings

observed in both hemophagocytic syndrome and immune deficiency (Guan et al 2020b, Lippi et al 2020, Wu et al 2020).

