**Table 8 9-point Category Ordinal Scale**

Scale	Description
4	Hospitalized – mild disease, oxygen by mask or nasal prongs
5	Hospitalized – severe disease, non-invasive ventilation or high flow oxygen
6	Hospitalized – severe disease, intubation and mechanical ventilation
7	Hospitalized – severe disease, ventilation and additional organ support, such as pressors, renal replacement therapy, extracorporeal membrane oxygenation
8	Death

a Score of zero on 9-point category ordinal scale will not be evaluated in this study.

To be considered a “responder” to treatment with a target candidate, a participant needs to show an improvement of at least 2 points (from first dose) on this scale. Time to clinical improvement of 2 points will be assessed as a secondary endpoint.

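### The responder definition has no survival condition, so a participant who improves by 2 points and then dies on or before Day 28 still counts as a responder

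*Protocol*

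**What the plan says.** Section 9.4.4.3 begins "Time to improvement defined as time to clinical improvement of at least 2 points (from first dose date) on a 9-point category ordinal scale". It adds two further triggers, live discharge and fitness for discharge (score 1 or 2), and takes the event as "whichever comes first, by Day 28". The same sentence says that this event also defines who is a responder "for the response rate analyses". The efficacy paragraph of the Synopsis repeats this. Section 8.1.1.2, below Table 8, gives a shorter rule: "a participant needs to show an improvement of at least 2 points (from first dose) on this scale".

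Neither section says that a responder must be alive at Day 28, or what happens to responder status after a later death. The censoring rules in Section 9.4.4.3 deal only with participants who had no improvement. Under the Schedule of Activities the scale is scored daily until discharge, at Day 14 or discharge, and at Day 28. Survival status is collected at Day 14 or discharge, Day 20, Day 28 and the safety follow-up.

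Section 9.4.4.1 treats the companion endpoint differently. There, only the participant's survival and respiratory failure "status on Days 14 and 28 will be considered for this endpoint".

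**The concern.** A response rate by Day 28 is naturally read as the share of participants who did well by Day 28. Under the stated rule it is the share who ever had a qualifying improvement, including any who then deteriorated and died inside the same 28 days. Both this endpoint and the one in Section 9.4.4.1 serve the single secondary objective of preliminary efficacy in Table 3, and the protocol has no rule to reconcile them when they classify the same person in opposite ways. The study has no control arm, so nothing offsets the misclassification, and it can only make the response rate look better.

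**Working it through.** The protocol states no expected response rate, so there is no figure of its own to reproduce. The check is a reading of the definitions followed by a count.

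**Inputs**
- n is about 20 (Section 9.2). Efficacy analyses use everyone who received at least one dose (Table 9).
- Table 8: score 8 is death, score 6 is "Hospitalized – severe disease, intubation and mechanical ventilation", and score 4 is "Hospitalized – mild disease, oxygen by mask or nasal prongs".
- Background mortality is nearly 50% among patients requiring mechanical ventilation (Section 2.2.1).
- The fraction of deaths that follow a recorded improvement is not in the protocol. Any value is an assumption.

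**Step 1: which trigger decides.** Inclusion criterion 4 requires respiratory failure before enrollment, so participants should normally start at 5, 6 or 7. A 2-point improvement then means a score of at most 3, 4 or 5 respectively. Reaching 2 from a start of 5, 6 or 7 is a drop of 3, 4 or 5 points. The 2-point trigger is therefore met before, or together with, the discharge triggers, and it has no survival condition.

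**Step 2: a worked case.** Take a participant who scores 6 at first dose and 4 on Day 8, is re-intubated on Day 11 and dies (score 8) on Day 20.
- Sections 9.4.4.3 and 8.1.1.2: 6 − 4 = 2 points on Day 8, so the event time is Day 8 and the participant is a responder. Nothing reverses this.
- Section 9.4.4.1: the participant is not alive on Day 28, so is a failure.

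**Step 3: size per case.** 1/20 = 5 percentage points. For scale, the standard error of a 50% rate is √(0.5 × 0.5/20) = 11.2 points.

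**Step 4: number of cases, by assumption only.** Cases = deaths × fraction of deaths that follow an improvement; shift = cases/20.
- 10 deaths (nearly 50% of 20, applied to everyone) with an assumed 10%, 20% or 30%: 1, 2 or 3 cases, or 5, 10 or 15 points.
- 6 deaths with the same fractions: 0.6, 1.2 or 1.8 expected cases, or 3, 6 or 9 points.
- 5 deaths (25% of 20) with the same fractions: 0.5, 1 or 1.5 expected cases, or 2.5, 5 or 7.5 points.
- A fraction of zero: no shift.

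**Step 5: illustration.** Suppose 12 of 20 are responders under the stated rule and two of them die by Day 28. The 90% interval is p ± [1.645 × √(p(1 − p)/n) + 1/(2n)], the Wald form with continuity correction that Section 9.4.4.1 names for its own endpoint, borrowed here.
- 12/20: 0.60 ± (1.645 × 0.1095 + 0.025) = 0.60 ± 0.205, or 39.5% to 80.5%.
- 10/20: 0.50 ± (1.645 × 0.1118 + 0.025) = 0.50 ± 0.209, or 29.1% to 70.9%.

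**The case against.** The strongest reply is that time to first improvement is a coherent endpoint, that Section 9.4.4.1 answers the survival question beside it, and that the two differ because they measure different things. This stands for the Kaplan-Meier analysis, which need not change. It does not rescue the response rate, which takes over the first-event definition and has no time axis to show that the improvement was lost.

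A second reply is that the unseen SAP may handle deaths after improvement. The protocol does not leave the definition open, however: it states who is a responder in two sections. A survival condition in the SAP would change that definition rather than fill a gap.

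A third reply concerns importance, and it stands. The response rate is not listed in Table 3. It is a descriptive by-product of one of three secondary endpoints in a single-arm study whose primary aims are pharmacokinetics and safety, with no formal efficacy test. Deaths by Day 28 are already visible in the endpoint of Section 9.4.4.1.

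A reader might go further and infer that every participant whose ventilator is withdrawn for comfort care becomes a responder, and that Section 9.4.4.1 must change because such a person could be alive and off support on Day 14 or 28. The protocol does not support this. It never mentions withdrawal of support. Rows 3 and 4 of Table 8 also specify mild disease, so a scorer could decline to use them, and death before the next daily score would give 8 with no drop recorded. The Section 9.4.4.1 case needs survival off support on exactly the assessment day. At most, a score drop after withdrawal of support can be recorded as an improvement.

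**Conclusion.** The point holds for deaths after a recorded improvement. Under Sections 9.4.4.3 and 8.1.1.2 a participant who improves and then dies on or before Day 28 is a responder, and under Section 9.4.4.1 the same participant is a failure at Day 28. Each case is worth 5 percentage points at about 20 participants, always in the favourable direction.

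The total effect cannot be derived from the protocol. The shifts in Step 4 rest on an assumed 10% to 30% of deaths following an improvement, which has no source in the protocol. A reader might also take the nearly 50% mortality as the rate for this trial. It refers to ventilated patients and is not tied to Day 28. Inclusion criterion 4 also admits high-flow oxygen and noninvasive ventilation, and exclusion criterion 3 removes patients expected to die within 24 hours. The 10-death scenario is therefore better read as an upper illustration than as a forecast.

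**What to change.** In Sections 9.4.4.3 and 8.1.1.2, state that a participant who dies on or before Day 28 is a non-responder in the response rate analysis, even if an improvement was recorded before death. Align the Synopsis, which repeats the responder definition.

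Word the rule by known death, not by being alive at Day 28. Improved participants whose Day 28 status is unknown, such as those withdrawn after a positive hepatitis result (Section 7.2) or lost to follow-up (Section 7.3), then keep their classification. This matters because Section 9.4.1 rules out imputation for efficacy.

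Leave the Kaplan-Meier analysis as time to first improvement, label it so, and report beside it the number who improved and later died by Day 28. Section 9.4.4.1 needs no change, and no comfort-care scoring rule is needed.

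The cost is a sentence in each place and one extra count in the report. Survival status is already collected at Day 28, so no new data are needed. The response rate may come out slightly lower, and responder status will no longer match the Kaplan-Meier event exactly, which the text should say.

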### **8.3.7 Disease Progression**

Disease progression can be considered as a worsening of a participant's condition attributable to COVID-19 pneumonia for which the study intervention is being studied. It may be an increase in the severity of the disease under study and/or increases in the symptoms of the disease. Events, which are unequivocally due to COVID-19 pneumonia, should not be reported as an AE or SAE during the study. Events attributable to disease progression of COVID-19 include pulmonary failure, acute respiratory distress syndrome, sepsis, shock, multiorgan failure and death.

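### Section 9.4.4.3 does not say how deaths without improvement are censored; if they are handled as dropouts, the Kaplan-Meier improvement estimate is biased upward

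*Protocol*

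**What the plan says.** Section 9.4.4.3 counts as an event a gain of at least 2 points on the 9-point scale or either of two discharge outcomes: "live discharge from the hospital, or considered fit for discharge (a score of 1 or 2 on the ordinal scale), whichever comes first, by Day" (the cut-off is Day 28). Death is not an event. The analysis is the "Kaplan-Meier method with Kaplan-Meier estimates and their 90% confidence intervals".

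Participants without an event fall into one of two branches:

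- Stayed in: a participant who "did not have an improvement and did not drop out prior to Day 28, the data will be censored at Day 28".
- Dropped out: for a participant who left before Day 28 without improving, "the data will be censored at the last date known that without improvement".

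The section does not mention death, although death is category 8 of the scale (Table 8). Three other places bear on how a reader would fill the gap:

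- Section 9.2 sets the enrolment target "allowing for ~25% dropout rate due to disease progression".
- Section 8.3.7 states: "Events attributable to disease progression of COVID-19 include pulmonary failure, acute respiratory distress syndrome, sepsis, shock, multiorgan failure and death".
- Section 2.2.1 gives the only relevant mortality figure: "The mortality rate in critically ill patients with COVID-19 (ie, those requiring mechanical ventilation) is nearly 50" per cent.

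**The concern.** Kaplan-Meier assumes that a censored participant has the same future chance of the event as those still under observation. A participant who has died cannot improve. Censoring at or before death removes that person from the denominator and shares the lost probability among the survivors. The estimated proportion improved can then only be too high or, at best, unchanged. The median shortens in the same direction, and the 90% interval is centred on the wrong value.

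The stated secondary objective is preliminary efficacy, and there is no control arm in which the same bias could cancel. Two analysts could also apply Section 9.4.4.3 to the same data in good faith and report materially different improvement curves.

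**Working it through.** The protocol states no figure for this endpoint, so there is none to reproduce. The check asks how far the two readings of the rule differ.

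**Inputs.** From the protocol: Kaplan-Meier to Day 28, the two censoring branches, and about 20 participants. Assumed: 40% truly improved by Day 28 (range 30% to 45%), mortality without improvement of 10% to 50%, constant hazards for both, and no other dropout.

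**Formulas.** Let p be the true proportion improved and d the proportion dead without improvement by Day 28.

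- Total cumulative hazard: H = −ln(1 − p − d)
- Improvement share: H1 = H × p/(p + d)
- Estimate with deaths censored at death: 1 − exp(−H1)
- Estimate with deaths kept in the risk set to Day 28: p

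**Worked case,** p = 0.40, d = 0.25: H = −ln(0.35) = 1.050; H1 = 1.050 × 0.40/0.65 = 0.646; 1 − exp(−0.646) = 0.476.

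| Mortality d | H | H1 | Deaths censored at death | Deaths kept to Day 28 | Excess (points) |
|---|---|---|---|---|---|
| 10% | 0.693 | 0.555 | 42.6% | 40% | 2.6 |
| 20% | 0.916 | 0.611 | 45.7% | 40% | 5.7 |
| 25% | 1.050 | 0.646 | 47.6% | 40% | 7.6 |
| 30% | 1.204 | 0.688 | 49.7% | 40% | 9.7 |
| 40% | 1.609 | 0.805 | 55.3% | 40% | 15.3 |
| 50% | 2.303 | 1.023 | 64.1% | 40% | 24.1 |

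For true improvement of 30% to 45%, the excess is 1.8 to 3.0 points at 10% mortality, 5.3 to 8.9 at 25%, 10.3 to 18.4 at 40% and 15.3 to 30.8 at 50%.

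**Median.** It is reached only when H1 is at least ln 2 = 0.693. With deaths censored at death that happens at 40% mortality (28 × 0.693/0.805 = 24.1 days) and at 50% (28 × 0.693/1.023 = 19.0 days). With 40% true improvement, no median exists by Day 28.

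**Check without the hazard assumption.** Take 20 participants, 8 of whom improve between Days 6 and 26.

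- 5 deaths, all before Day 6: 8/15 = 53%. Spread over follow-up: 48%.
- 10 deaths, all before Day 6: 8/10 = 80%. Spread over follow-up: 67%.
- All deaths after the last improvement, or all deaths censored at Day 28: 8/20 = 40%.

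The bias therefore depends on the number and timing of deaths and vanishes under the Day-28 reading.

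**The case against.** A reader might infer that the protocol actually sends deaths to censoring at the last date without improvement. The text does not say so. Taken literally, someone who died did not drop out and belongs in the Day-28 branch, which gives no bias. Other passages support that reading. Section 7.3 says a participant found to be deceased is not lost to follow-up. Sections 4.4 and 7.1 list death separately from withdrawal of consent and loss to follow-up. Table 8 makes death an observed state. The dropout in Section 9.2 concerns reaching PK Visit 2, and Section 8.3.7 is a rule for adverse-event reporting. All of this stands, so assigning deaths to the dropout branch is an inference. What remains is that the rule supports both readings and they give different answers.

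A reader might also infer a trial population with about 50% mortality. Section 2.2.1 ties that figure to mechanically ventilated patients. Section 5.1 also admits patients on high-flow oxygen or non-invasive support, and Section 5.2 excludes those expected to die within 24 hours. The 64% row is therefore an upper scenario.

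The SAP, which is not at hand, may settle the matter; Section 9.4 promises more detail there. But the protocol wrote the censoring rule itself and left out the main competing event, so a SAP that follows it faithfully starts from an incomplete rule.

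Finally, the endpoint is secondary, no efficacy hypothesis is tested (Section 9.1), and sampling error is large. At 40% with 20 participants the standard error is √(0.4 × 0.6/20) = 11 points, above the 7.6-point excess at 25% mortality. This lowers the severity but does not remove the bias, which always runs in the same direction.

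**Conclusion.** The point holds as an ambiguity with a material consequence under one plausible reading. Section 9.4.4.3 fixes a two-branch censoring rule and does not place deaths in either branch. If deaths are treated as dropouts, a true 40% improvement would be reported as about 43% at 10% mortality, 48% at 25%, 55% at 40% and 64% at 50%. These figures rest on constant hazards, no other dropout and assumed rates. If deaths are censored at Day 28, the excess is zero.

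The documents do not establish that the biased reading is the intended one, nor what mortality to expect across the eligible population. Only the Kaplan-Meier curve, its median and its interval are exposed. In the responder proportion over all treated participants, a death before improvement is simply a non-responder, and the endpoint in Section 9.4.4.1 already requires being alive. Severity: moderate.

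**What to change.** In Section 9.4.4.3, and in the efficacy paragraph of the synopsis, add one of the following:

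- Participants who die without improvement are non-improvers; they stay in the risk set and are censored at Day 28 whatever the date of death.
- Improvement is estimated as a cumulative incidence with death as a competing event (Aalen-Johansen), with its 90% confidence interval.

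In either case, reserve censoring at the last date without improvement for participants who leave the study alive. The two options coincide exactly only when nobody is censored early for another reason, so name one of them as the analysis.

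The cost is one sentence in the protocol and the matching line in the SAP. No new data are needed: Table 1 schedules the ordinal scale daily until discharge, as well as survival status. Those are safer sources for the date of death than serious adverse event forms, because Section 8.3.7 keeps events unequivocally due to COVID-19 pneumonia out of that reporting. Compared with censoring at death, the reported improvement rate may be less favourable.
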